Transcutaneous Electric Nerve Stimulation For
Pain Control During Office Intra-detrusor
Onabotulinumtoxin A Cystoscopy Injection for
Overactive Bladder: A Phase III Randomized
Controlled Trial

NCT04448171

08Sep2023

TRANSCUTANEOUS ELECTRIC NERVE STIMULATION FOR
PAIN CONTROL DURING OFFICE INTRA-DETRUSOR
ONABOTULINUMTOXIN A CYSTOSCOPIC INJECTION FOR
OVERACTIVE BLADDER: A PHASE III RANDOMIZED
CONTROLLED TRIAL

Principal Investigator: **[name] MD MS FPMRS**
Division of Urogynecology
Department of Gynecologic Surgery
[name]

Co-Investigators: [name] MD
[name] MD MS FPMRS
[name] MD MS FPMRS
[name] MD MS FPMRS

Statistician: [name] MS

Protocol Number: 20-003510

Version 1.0: 06-April-2020
Version 1.1: 08-Sep-2020
Version 1.2: 28-April-2021
Version 1.3: 08-Sep-2023

Study Summary

Title	Transcutaneous Electric Nerve Stimulation For Pain control During Office Intra-detrusor Onabotulinumtoxin A Cystoscopy Injection for Overactive Bladder: A Phase III Randomized Controlled Trial
Running Title	TENS Units for Pain Control During Office Cystoscopic Botox Injections
Protocol Number	20-003510
Phase	Phase III
Methodology	Two Arm Phase III Double Blinded Randomized Placebo Controlled Trial
Overall Study Duration	12 months
Subject Participation Duration	2 days
Single or Multi-Site	Single Site
Objectives	Primary Objective(s): To determine the effect of Transcutaneous Electric Nerve Stimulation (TENS) units on pain experienced by women undergoing office cystoscopic intradetrusor onabotulinumtoxin A injection for overactive bladder
Number of Participants	60
Diagnosis and Main Inclusion Criteria	
 1. Age ≥ 18 2. Scheduled to receive Intradetrusor Onabotulinumtoxin A injection for Overactive Bladder 3. English speaking
Study Product, Dose, Route, Regimen	
Product: TENS Unit
 
Dose: Asymmetric, balanced, biphasic square waveform at a mixed stimulating frequency that randomly varying between 80 and 100 Hz and a pulse duration of 300 microseconds
 
Route: Transcutaneous using Adhesive Pads

Duration of Administration	To start 5 minutes before the procedure and during the procedure
Reference therapy	Current Standard of Care: Intra-urethral Lidocaine, Intra-vesicle Lidocaine Solution, Distraction techniques, Aromatherapy
Statistical Methodology	The data will be analyzed using an intention-to-treat approach. In order to account for individual participant pain sensitivity profiles through the experiment, random effect longitudinal model will be adjusted to the data controlling by treatment and selected covariates at baseline.

1 Introduction:

This document is a protocol for a human research study. This study will be carried out in accordance with the applicable United States government regulations and Mayo Clinic research policies and procedures.

1.1 *Background*

Options for adequate pain control during office-based cystoscopy procedures are limited [1]. Currently, varying pain control strategies are being used including local anesthesia (intra-urethral lidocaine [2], intra-vesicular lidocaine solution[1, 3]), distraction techniques[2, 4] (conversation/music/’squeeze balls’), aromatherapy[5], intramuscular analgesia, sedation and a combination of these techniques. Despite this, participants often experience pain during the procedure. Trans-cutaneous Electrical Nerve Stimulation (TENS) is a non-pharmacologic, non-invasive and safe method of pain control that involves delivery of electrical impulses to the skin, resulting in a reduction in perceived pain. TENS units have been successfully used for intraoperative pain control during office hysteroscopy[6] and office colonoscopy[7]. They may also help reduce pain during cystoscopy. Overactive bladder (OAB) is a symptom complex pronounced by urinary urgency, affecting up to 12% of the adult population, with a significant negative impact quality on the life [8]. Cystoscopic Intradetrusor Onabotulinumtoxin A is used for the treatment of OAB in participants who do not tolerate or adequately respond to oral anticholinergic medications[9]. The response to the onabotulinumtoxin A injection is transient and requires repeat injections roughly every 6-7 months. Adequate pain control during this procedure is essential for success in the office setting [10, 11]. There is a critical need to assess the effectiveness of TENS units for intraoperative pain management during office cystoscopic Intradetrusor Onabotulinumtoxin A. In the absence of such knowledge, the realization of the pain control potential of TENS units during office cystoscopy will remain unknown.

1.2 *Overactive Bladder and Cystoscopic Intradetrusor Onabotulinumtoxin A*

Overactive bladder (OAB) is a symptom complex that includes urinary urgency, frequency, urgency incontinence, and nocturia. It is highly prevalent, affecting up to 12% of the adult population, and can significantly impact quality of life (8). In 2013, FDA approved Intradetrusor Onabotulinumtoxin A for the treatment of overactive bladder symptoms in patients who do not tolerate or adequately respond to oral anticholinergic medications(9). Of note more than 50% patients starting medical therapy discontinue medical therapy by 6 months(13). The therapy is performed by a cystoscopic injection that can be carried out in an office setting with topical analgesia or under sedation in the operating room. The response to the onabotulinumtoxin A injection is transient, requiring repeat injections roughly every 6-7 months (10, 11). Due to the need for repeat injections, performing this procedure in the office is cost effective (14). Adequate pain control during this procedure is essential for success in the office setting. A limited number of studies have looked at measures to improve pain control with office cystoscopic onabotulinumtoxin A injections. LeClaire et al. (2018), in a randomized control trial of 26 participants undergoing office cystoscopic onabotulinumtoxin A injection for overactive bladder randomized to a belladonna and opiate suppository group (n =13) and a placebo suppository group (n = 13), found that the belladonna and opiate did not significantly reduce bladder injection pain(1). Nambiar et al. (2016) in a randomized control trial of 54 participants undergoing office cystoscopic onabotulinumtoxin A injection for overactive bladder randomized to receive intravesical alkalinized lidocaine solution group (n =26) and intravesicle lidocaine gel (n = 28), found that alkalinized solution was not superior to lidocaine gel(3).

1.3 *Adequate Pain Control During Office Cystoscopy*

Operative office cystoscopy is a painful procedure and often results in preprocedural anxiety in patients (1-4). Flexible cystoscopy maybe less painful than rigid cystoscopy (4). Options for adequate pain control during office-based cystoscopy procedures are limited (1). Currently, varying pain control strategies are being used including local anesthesia (intra-urethral lidocaine (2), intra-vesicular lidocaine solution (1, 3), distraction techniques (2, 4) (conversation/music/'squeeze balls'), aromatherapy(5), intramuscular analgesia, sedation and a combination of these techniques. Despite these interventions, patients often experience mild to moderate amount of pain during the operative office cystoscopy (1, 3).

1.4 *Trans-cutaneous Electrical Nerve Stimulation (TENS) in an Office Setting*

Trans-cutaneous Electrical Nerve Stimulation (TENS) may provide satisfactory pain control in the office setting. It is easy to access and use following proper training. There is a lack of side effects compared to existing pharmacology pain control methods and the lack of need for in-office anesthesia personnel and prolonged post-procedural monitoring. There are limited studies looking

at TENS unit for intraoperative pain management. In order to get the best analgesic effect from the TENS unit, it is now known that accurate placement of electrodes, and selection of the appropriate current waveform, waveform duration, frequency and intensity are essential [6, 12]. With regards to electrode placement, it is important to place the electrodes near the nerves that supply the area where the analgesic effect is needed [6, 13]. Hruby et al (2016) in a randomized control trial of 148 patients in 2006 undergoing flexible cystoscopy showed no difference in mean visual analogue pain score between the no analgesia group, placebo TENS group and activated TENS (mean visual analogue pain score of 3.73, 3.65, 3.52 respectively, $p= 0.97$). In this study, the electrodes were placed halfway along an imaginary line between the anterior superior iliac spine and the pubis. Such a placement has been shown to be suboptimal in achieving pain control for pelvic procedures. Also, in this study the pulse duration was set at 180 microsecond pulse width. The current consensus is the pulse duration of greater than 250 microseconds is important to achieve adequate analgesia [6, 13]. Studies have shown a reduction in pain with the appropriate use of TENS units during office hysteroscopy[6] and during colonoscopy[7].

1.5 *Innovation*

The long term goal is to contribute towards effective pain control strategies for office based operative procedures. Our overall objective in this application is to determine how TENS units affect pain control during office cystoscopic Intradetrusor Onabotulinumtoxin A injections. This will be the first study looking at the effectiveness of TENS units for pain control during office cystoscopic Intradetrusor Onabotulinumtoxin A injections. It will also be the first study looking at the effectiveness of TENS units for pain control during office cystoscopy in general, using appropriate TENS settings. The knowledge gained from this study will have widespread implications for pain control during office based cystoscopic procedures in the field of Urogynecology and Urology, and can be extrapolated to other office based procedures in other fields as well. If TENS units prove to be effective in pain control for office based procedures, this will lead to a paradigm shift.

1.6 *Choosing the Specific Aims of this Study:*

Prior to 2017, we performed all cystoscopic Onabotulinum Toxin A injections in the operating room at Mayo Clinic in Rochester, Minnesota. Patients with refractory overactive bladder require repeat injections and had to return to the operating room on average every 6-7 months. This would be almost a whole day's ordeal for patients. In order to minimize the inconvenience to patients and to provide cost effective patient care, Cystoscopic Onabotulinum A injections were transitioned to the office setting in 2017.

For successful adoption of office cystoscopic Onabotulinum Toxin A injection, the procedure has to be an acceptable option to patients. As noted earlier, office cystoscopy in itself is an uncomfortable procedure and the addition bladder injections make it painful. The pain patients experience during the procedure can deter them from wanting a repeat cystoscopic injection in office setting. Currently we use local anesthesia (intra-urethral lidocaine), intra-vesicular lidocaine solution, distraction techniques (conversation/music/’squeeze balls’), and aromatherapy for pain control during this procedure. Despite this, a preliminary review of 91 office Cystoscopic Onabotulinum A injections performed at our institution from 2017 to 2019 showed that the average intra-procedural pain score was 5 on a numerical pain scale of 0 to 10.

Therefore, we chose the pain experienced during the office Cystoscopic Onabotulinum Toxin A injection and the patient’s satisfaction from the procedure as the specific aims for this study.

2 Study Objective(s)/Aims(s):

2.1 *Specific Aim #1: To assess whether the TENS units are effective for intraoperative pain management during office cystoscopic Intradetrusor Onabotulinumtoxin A in women with OAB.*

We plan to compare participant reported pain using a 0-10 numerical pain scale at baseline, during and after cystoscopic intradetrusor onabotulinumtoxin A injection in patients randomized to active TENS units and placebo TENS units. We will compare the change in numerical pain scale from baseline to intraoperatively and intraoperatively to postoperatively between both groups.

[figure not shown]
2.2 *Specific Aim #2: To evaluate the effect of TENS units on participant satisfaction following cystoscopic intradetrusor onabotulinumtoxin A injection in women with OAB.*

We plan to evaluate participant satisfaction on a 10 point Likert scale immediately after the procedure in participants randomized to activated TENS units and placebo TENS units.

3 Study Design

3.1 *General Description*

The study is a two arm phase III double blinded randomized placebo control trial looking at the effect of TENS unit on pain in participants receiving Office based Cystoscopic Onabotulinum Toxin A injection for Overactive bladder at the Mayo Clinic in Rochester, Minnesota.

3.2 Number of Subjects: 60 subjects**3.3 Duration of Participation:** From accrual to the end of the Cystoscopic Onabotulinum Toxin A injection office visit**3.4 Study Schema and Flow:**

3.5 Primary endpoints

- Numeric Analog Pain Score (0-10) at Baseline before Office Cystoscopic Onabotulinum Toxin A injection (collected after the participant changes into procedural gown)
- Numeric Analog Pain Score (0-10) during Office Cystoscopic Onabotulinum Toxin A injection (collected during middle of the procedure, after the 10th injection)
- Numeric Analog Pain Score (0-10) after Office Cystoscopic Onabotulinum Toxin A injection (collected 5-10 minutes after the procedure)

Source: The Numerical Analog Pain Score will be documented by the study coordinator into the case report forms and later transferred in the Red Caps Data Management system.

3.6 Secondary Endpoints

- Participant satisfaction on a Likert Scale of 1 - 10 (10 = Completely satisfied and 1 = Completely Dissatisfied) after the Office Cystoscopic Onabotulinum Toxin A injection (collected 5-10 minutes after the procedure)
- Depression Screen Score (PHQ 9)
- Anxiety Screen Score (GAD 7)
- History of Sexual Abuse
- History of Chronic Pelvic Pain
- Participant Demographics: Age, Ethnicity, Basal Metabolic Index (BMI), Insurance
- Co-morbid conditions
- Current Medications
- Smoking Status
- Past or Current Illicit Drug Abuse
- Presence of Chronic Pain
- Number of Previous Onabotulinum Toxin A injection
- Previous Therapies for OAB (Lifestyle, Medication, Peripheral Tibial Nerve Stimulation, Sacral neuromodulation)

Source: The Participant Satisfaction Score, PHQ 9 score and GAD 7 score will be documented by the study coordinator into the case report forms and later transferred in the REDCap Data Management system. The participant demographics, co-morbid condition, current medications, smoking status, history of past or current illicit drug abuse, presence of chronic pain, number of previous Onabotulinum Toxin A injections, and previous therapies for OAB will be extracted from the electronic medical records. This information will be transferred to the REDCap Data Management System by the Principal and Co-investigators on the study.

4 Subject Selection Enrollment and Withdrawal

4.1 Inclusion Criteria

- Age 18 and older
- Scheduled to receive Intradetrusor Onabotulinumtoxin A injection
- English speaking

4.2 Exclusion Criteria

- Unable or Declining to Give Informed Consent
- Allergy to adhesives
- Participant self-report of previous use of TENS Unit within 1 year prior to study enrollment.
- Fitted with pacemaker or automatic implanted cardiac defibrillator
- History of Epilepsy
- Pregnancy and Postpartum period (within 12 weeks postpartum)

4.3 Subject Recruitment, Enrollment

All women with a diagnosis of Overactive bladder who are pursuing Office Cystoscopic Onabotulinum Toxin A for treatment and receiving care at the Division of Urogynecology, Mayo Clinic in Rochester, Minnesota will be approached for this study. Fellows, residents, Advanced level providers and Urogynecologists can offer these participants to talk with the study coordinator. The study coordinator will then be notified of women with Overactive Bladder interested in office based Cystoscopic Intra-detrusor Onabotulinum Toxin A injections by the care provider/Registered Nurse during the office visits following their appointment. The study coordinator will then approach the women interested in the study immediately following this appointment. The study coordinator will make sure that the participant meets the inclusion and exclusion criteria for the study. A written informed consent will be obtained from all eligible women who chose to participate using a standardized consent form approved by the Mayo Clinic Institutional Review Board. We will allow for 1 year from the start of recruitment for accrual of participants, expecting to enroll approximately 5 participants per month. A total of 60 participants will be recruited with 30 participants in each group (Active TENS group and Sham TENS group).

4.4 Withdrawal of Subjects and Follow up

A participant can chose to withdraw from the study at any point. A verbal request is all that is needed and can be conveyed to anyone of the team members taking care of the participant. This information will then be relayed to the study coordinator by the person receiving the request. No further follow up is needed.

5 Study Procedures

A flow chart of study activities is provided in Protocol Section 3.4

5.1 *Visit 1:*

Participants will be recruited from the Division of Urogynecology at Mayo Clinic, where care is being provided. Care providers will determine whether women are interested in learning about the study. The study coordinator will then be notified of women with Overactive Bladder interested in office based Cystoscopic Intra-detrusor Onabotulinum Toxin A injections by the care provider/Registered Nurse during the office visit following their appointment. The study coordinator will then approach the women interested in the study immediately following this appointment. A written informed consent will be obtained from all eligible women who chose to participate using a standardized consent form approved by the Mayo Clinic Institutional Review Board. We will allow for 1 year from the start of recruitment for accrual of participants.

5.2 *Outpatient Procedure Visit: Cystoscopic Onabotulinum Toxin A Injection*

On the day of the scheduled procedural visit, all participants will receive a Generalized Anxiety Disorder 7 (GAD -7) and Depression screening questionnaire (PHQ-9). Those women screening positive for anxiety (GAD 7 score ≥ 10) or depression (PHQ-9 score ≥ 10), will be offered referral to their primary care provider for further management. These women can continue to remain in the study and will not be excluded. In the same questionnaire, the participants will be asked “Have you ever experienced sexual abuse?” in order to assess for a history of sexual abuse. Participants will also be asked “Have you experienced chronic, unrelenting pain for 6 months or more duration?” in order to assess for a history of chronic pain.

Participants will be randomized to two groups using a computerized sequence generator based on permuted block randomization (1:1 allocation ratio) on the day of the procedure by the registered nurse (RN) taking care of the participant. Participants in Group 1 will receive an Activated TENS unit for pain control. Participants in Group 2 will have a Sham, inactive TENS unit for pain control. Both groups will be blinded to the type of TENS unit received. The nursing team taking care of the participant will know about the randomization. The care providers performing the procedure and the study coordinator will not be notified about the randomization.

On the day of the procedure, after baseline questionnaires and randomization, the participant will receive intraurethral lidocaine jelly as part of the standard pain control measures. Her bladder is then emptied using a Foley Catheter, and at the same time the bladder is then backfilled with 30 ml (300 mg/30 ml) of 1 % plain lidocaine solution. A waiting period of 30-50 minutes duration is allowed for the intravesicle lidocaine to take effect. During this wait period, participant is asked to lie supine for 10-15 minutes, then roll to the left side for 10-15 minutes and then to right side for about 10-15 minutes.

The participant, the provider taking care of the participant and the study coordinator assigned to the study will be blinded to the randomization. Both groups of participants will receive the TENS unit electrode placement during this wait period by the RN.

In participants randomized to the Active TENS group, the TENS unit will be initiated on standard setting (see ‘TENS, Electrode Placement, and Settings’) 5 minutes before starting the cystoscopy and will last the duration of the cystoscopy. The device intensity (amplitude) will be individually adjusted to each participant’s maximum sensory level, which is the strongest reported tingling feeling without pain and muscle contractions and kept at this setting for the duration of the procedure.

Participants randomized to the Sham TENS group will not receive the TENS therapy. Instead, they will receive electrode placement followed by initiation of the TENS unit until the participant feels the tingling sensation, following which the TENS unit will be immediately turned off by the RN. The participant will be notified by the RN that the TENS stimulus has been turned down such that they are not able to feel the tingling sensation anymore.

Following the initiation/placement of the TENS unit, the study coordinator and fellowship trained Urogynecologist will enter the room. Rigid cystoscopic Intradetrusor Onabotulinumtoxin A injection will be performed by a fellowship trained Urogynecologist. This involves 100 units of Onabotulinumtoxin A injected in roughly 20 aliquots throughout the bladder. After the procedure participants are discharged home.

Care providers performing the injection will only be allowed into the procedure room once the TENS units has been activated. The nursing staff will assess the pad placement sites for any skin irritation, and or burns. If so, this will be documented on the participant’s electronic medical record. The study coordinator will ask the participant and the provider separately (in the absence of the other) whether they felt the participant was in the Active TENS group versus the Sham TENS group at the end of the procedure. Participants will be advised to call and inform the clinic if they experience any burns, skin irritation or muscle soreness/pain.

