And/or per protocol may be problems/events that in the opinion of the sponsor-investigator may have adversely affected the rights, safety, or welfare of the subjects or others, or substantially compromised the research data.

Other important medical events are those that may not be immediately life threatening, but are clearly of major clinical significance include:

- Burns
- Skin Irritation
- Muscle Pain or Soreness

All adverse events that do not meet any of the criteria for serious, should be regarded as **non-serious adverse events**.

Adverse Event Reporting Period

For this study, the study treatment follow-up period is defined as from enrollment to 1 week after receiving the cystoscopic Onabotulinum Toxin A injection.

Preexisting Condition

A preexisting condition is one that is present at the start of the study. A preexisting condition should be recorded as an adverse event if the frequency, intensity, or the character of the condition worsens during the study period.

General Physical Examination Findings

At screening, any clinically significant abnormality should be recorded as a preexisting condition. At the end of the study, any new clinically significant findings/abnormalities that meet the definition of an adverse event must also be recorded and documented as an adverse event.

Post-study Adverse Event

All unresolved adverse events should be followed by the sponsor-investigator until the events are resolved, the subject is lost to follow-up, or the adverse event is otherwise explained. At the last scheduled visit, the sponsor-investigator should instruct each subject to report, to the sponsor-investigator, any subsequent event(s) that the subject, or the subject's personal physician, believes might reasonably be related to participation in this study.

Abnormal Laboratory Values

No abnormal laboratory values are related to the administration of the TENS Unit

Hospitalization, Prolonged Hospitalization or Surgery

Any adverse event that results in hospitalization or prolonged hospitalization should be documented and reported as a serious adverse event unless specifically instructed otherwise in this protocol. Any condition responsible for surgery should be documented as an adverse event if the condition meets the criteria for an adverse event.

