7.2 Recording of Adverse Events

At each contact with the subject, the study team must seek information on adverse events by specific questioning and, as appropriate, by examination. Information on all adverse events should be recorded immediately in the source document, and also in the appropriate adverse event section of the case report form (CRF). All clearly related signs, symptoms, and abnormal diagnostic, laboratory or procedure results should be recorded in the source document.

All adverse events occurring during the study period must be recorded. The clinical course of each event should be followed until resolution, stabilization, or until it has been ultimately determined that the study treatment or participation is not the probable cause. Serious adverse

events that are still ongoing at the end of the study period must be followed up, to determine the final outcome. Any serious adverse event that occurs during the Adverse Event Reporting Period and is considered to be at least possibly related to the study treatment or study participation should be recorded and reported immediately.

CTCAE Version 5.0 (November 27, 2017) will be used for classification and grading of Adverse Events:

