7.1 Stopping Rules

An interim analysis will be performed after 30 participants have undergone cystoscopic Onabotulinum Toxin A injection as part of the study. The information will also be sent to an internal reviewer (as appointment by the Mayo Clinic Obstetrics and Gynecology Department Research chair). At this point a meeting between the investigators and internal reviewer will be convened to discuss the existing data, the efficacy and any safety issues including serious adverse events that have taken place. A decision will be made as to whether to continue with the study or to prematurely terminate the study based on any safety issues.

If there are greater than 3 serious adverse (i.e. severe skin reactions, burns, muscle weakness) events reported in the 30 participants reviewed, further recruitment and administration of the TENS unit will be stopped. The study will be put on hold with the IRB and each of the adverse events will be carefully looked into for any causal relation to the TENS unit. If no causal relationship is proved then the will re-approach IRB for restarting the study.

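### Pad-site harms are charted only when found, by nurses who know the arm, and no harm summary by arm is prespecified

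*Combined protocol and SAP*

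**What the plan says.** In Section 5.2 (Outpatient Procedure Visit) the registered nurse randomizes the participant and places the electrodes in both arms. Of the nursing team it says: "The nursing team taking care of the participant will know about the randomization". The injecting provider, the study coordinator and the participant are blinded. The nursing team also makes the skin check: "The nursing staff will assess the pad placement sites for any skin irritation, and or burns. If so, this will be documented on the participant’s" chart. For later events the plan relies on the participant: "Participants will be advised to call and inform the clinic if they experience any burns, skin irritation or muscle soreness/pain".

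Section 7.1 (Definitions) lists burns, skin irritation, and muscle pain or soreness under this lead-in: "Other important medical events are those that may not be immediately life threatening, but are clearly of major clinical significance include". Section 7.2 (Recording of Adverse Events) sets a general duty: "At each contact with the subject, the study team must seek information on adverse events by specific questioning and, as appropriate, by examination". It requires every adverse event to reach the source document and the CRF, and Section 7.3.1 adds the data management system. Section 7.3 has the CRF's adverse event section completed once an event has been identified.

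Section 6 analyses pain and satisfaction only. Sections 3.5 and 3.6 list no safety endpoint. The one numerical harm rule, in Section 7.1 (Stopping Rules), is a hold trigger with no split by arm: "If there are greater than 3 serious adverse (i.e. severe skin reactions, burns, muscle weakness) events reported in the 30 participants reviewed".

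**The concern.** Both arms wear the same electrodes, but only the active arm has sustained stimulation. The sham arm is therefore what separates harm from stimulation from harm from the adhesive. For that comparison to be fair, harms must be looked for and written down in the same way in both arms.

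The pad-site check does not secure this, for two reasons. First, charting by exception leaves no trace of a negative check, so an empty record may mean clear skin or no inspection. Second, the person who decides whether a mild redness is worth charting knows whether the unit was on. That could raise recording in the active arm (more suspicion) or lower it (redness taken as normal under a working device), and the documents do not let one say which. Because Section 6 has no by-arm summary, the choice of what to tabulate, over which denominator, would be made after the data are seen.

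**Working it through.** **The plan's own figures.** The documents state no harm rate, harm precision or harm power. The only power figure is for pain, and it reproduces. With 27 per arm, difference 2.0 and SDs 2.0 and 3 (Section 6.1), the noncentrality is 2.0/√(4/27 + 9/27) = 2.882 on 45.3 Satterthwaite degrees of freedom, which gives 80.53% for a two-sided Welch test at 0.05. The 10% dropout allowance gives 27/(1 − 0.10) = 30 per arm. Neither figure is in dispute; 30 is the harm denominator used below.

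**Can a negative check be found in any record?**
- Section 5.2: charted in the medical record only if irritation or a burn is seen.
- Section 7.3: the CRF adverse event section is completed when an event has been identified.
- Section 8.3.1: data not on the CRF are abstracted from the medical record. This recovers charted positives, not uncharted negatives.
- Sections 8.3, 8.3.3 and 8.3.4: missing data are explained and CRFs are checked for completeness. These can flag a skipped check only if a field exists for every participant, and none is described.
- Schedule of Events (Section 5.3): no adverse event row.

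No described route records a negative or an omitted check.

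**What an omitted check does.** Suppose no event is charted among 30 active participants and m checks were omitted. The true count then lies between 0/30 and m/30. As an illustration take m = 3, which leaves 27 checked. The range is 0% to 3/30 = 10.0%. The exact (Clopper–Pearson) upper limit with no events is 1 − 0.025^(1/n):
- n = 30: 11.6%
- n = 27: 12.8%

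If the three omitted checks had all been positive, 3/30 has an exact 95% interval of 2.1% to 26.5%. As written, the data could not show which of these applies.

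**What unequal recording does.** Let p_A and p_S be the true event proportions, and c_A and c_S the probabilities that an event is recorded. The recorded difference has expectation p_A·c_A − p_S·c_S. If the true rates are equal at p, this is p(c_A − c_S), which is not zero when recording depends on the arm. Neither c can be estimated from charting by exception.

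**What a by-arm summary can deliver at 30 per arm.** Exact 95% intervals are 0 to 11.6% for 0/30, 0.1% to 17.2% for 1/30 and 2.1% to 26.5% for 3/30. The two-sided Fisher test gives p = 0.052 for 5/30 against 0/30 and p = 0.024 for 6/30 against 0/30. Under assumed true rates, its power is 4% for 10% versus 2%, 41% for 20% versus 2%, and 81% for 30% versus 2%. The summary should therefore describe, not test.

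**Time window.** Section 7.1 (Adverse Event Reporting Period) runs to one week after the injection. Section 3.3 ends participation with the injection visit, and the Schedule of Events has no later contact. Post-discharge events thus depend on the participant calling.

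**The case against.** The strongest reply is that nurse charting is not the only route. Section 7.2 requires specific questioning at each contact, all adverse events must be recorded, the coordinator is blinded, and soreness is reported by participants who are themselves blinded. That stands, and it defeats three stronger readings:

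- A reader might infer that the plan yields no harm rate for TENS. It does not follow. Allocation and the randomized denominators are known, and events must reach the database, so a crude rate per arm is computable after unblinding. What is missing is a prespecified summary and a record of who was assessed.
- A reader might infer that harms will be reported as one pooled rate over all 60 participants. No section proposes this. The count over 30 participants is a trigger for a hold and event-by-event review, not an estimate.
- A reader might infer that a by-arm table would test the background statement in Section 1.4 about side effects. That statement compares TENS with pharmacologic methods, which an active-versus-sham contrast cannot address.

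It is also fair to say that the CRF itself is not in the documents, so a yes/no field for every participant cannot be ruled out. But the text describes completion on identification of an event. If such a field exists, Sections 5.2 and 7.2 need only say so. Finally, safety is not an aim or an endpoint, and precision is low. That limits the claim to a descriptive one; it does not justify recording that can differ by arm.

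**Conclusion.** The point holds in a limited form. Harms must be sought and recorded, but the pad-site check is made by unblinded staff and charted by exception, and no harm summary by arm is prespecified. The table could be added later. A missing record of who was checked, and unequal charting, cannot be repaired once the trial is over.

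The documents do not fix the size. With 30 per arm and an illustrative three omitted checks, a report of no events could stand for anything from 0% to 10.0% in that arm. With complete recording, 0/30 still allows up to 11.6%. The direction of any bias from unblinded charting is unknown. This rests on reading Sections 5.2 and 7.3 as the full description of how findings are recorded. It does not affect the primary pain result, but it should be corrected, because the change is small and the loss is permanent.

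**What to change.** 1. **Recording (Sections 5.2 and 7.2).** Replace documentation only when something is found with a CRF entry for every participant, coded yes / no / not assessed, for burn and for skin irritation, taken from the existing nursing check. Have the blinded coordinator ask every participant about skin symptoms and muscle soreness at the existing contact 5–10 minutes after the procedure. These questions should come after the pain score, the satisfaction score and the arm-guess question, so that they cannot colour any of them. The coordinator should not see the nurse's entry before then.
2. **Analysis (Section 6).** Report burns, skin irritation, muscle pain or soreness, and any adverse event by arm: counts and percentages with exact 95% intervals, the number not assessed, and the active-minus-sham difference. State that this is descriptive, with no hypothesis test.
3. **Consistency.** Reconcile the one-week adverse event window in Section 7.1 with participation that ends at the visit (Section 3.3) and with a Schedule of Events that has no adverse event row or later contact. State how events after discharge are to be captured. The same-visit questions will not catch soreness that starts later.

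Cost: a few items on the existing CRF, one table and one paragraph in Section 6, and about a minute more per participant, with existing staff at existing contacts. The nursing check itself is unchanged. The intervals will be wide, and the report should say so.
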